6.5.4.3. Physical Examination

Physical examination results and Child Pugh scores (A[a score of 5 to 6], B[a score of 7 to 9], C[a score of 10 or above]) will be summarized by visit. Listings of physical examination and Child Pugh scores results will be produced.

6.5.4.4. Electroencephalogram

The number and frequency of subjects with EEG findings will be summarized by visit. All data from local interpretation of EEGs will be presented in by-subject listings.

Central EEG readings will be summarized in a separate report, if determined to be applicable.

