#### 2.2.1 Safety Endpoints

- Incidence and severity of AEs and serious adverse events (SAEs)
- Incidence of clinical laboratory abnormalities
- Change from baseline in clinical laboratory assessments
- Change from baseline in clinical findings from physical examination
- Change from baseline in vital sign measurements
- Change from baseline in EEG results

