### 13.7.2 Secondary Efficacy Analyses

The secondary efficacy endpoints include:

- Change from baseline in urine and blood SSC levels
- Change from baseline in clinical findings from neurologic examination
- Change from baseline in age-appropriate motor and cognitive assessments (Bayley--III, GMFCS, WPPSI)
- Change from baseline in seizure frequency
- Change from baseline in neuroimaging
- Changes in growth parameters (body weight, body length, head circumference)
- Change from baseline in feeding patterns

Baseline is defined as the last available assessment prior to treatment with ORGN001 except for blood and urine biomarkers whereby baseline is defined as the average of all available assessments prior to treatment with ORGN001.

Observed urine and blood SSC levels as well as changes and percentage changes from baseline to the study time points will be summarized. Individual patient plots over time will be produced.

Shifts from baseline in clinical findings from neurologic examination and neuroimaging findings will be presented for the different time points. The frequency of seizures will be summarized.

Observed values and changes in GMFCS, WPPSI, and Bayley-III cognitive, language, and gross and fine motor scores will be summarized.

Growth parameters (weight [kg], length [cm], and head circumference [cm]) will be converted to age-adjusted z-scores and descriptive statistics will be presented for each parameter over time. In addition, the following individual patient's growth charts will be produced as specified in the statistical analysis plan (SAP) with a flag for start of ORGN001 infusion: Weight-for-age percentiles, length-for-age percentiles and head circumference-for-age-percentiles.

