4. DEFINITIONS

4.1. Efficacy

There is no pre-specified primary efficacy endpoint in this study. The secondary efficacy endpoints at all key study timepoints include:

- Change from baseline in urine and blood [REDACTED] levels
- Change from baseline in clinical findings from neurologic examination
- Change from baseline in age-appropriate motor and cognitive assessments (Bayley Scales of Infant Development-Third Edition [Bayley-III], The expanded and revised Gross Motor Function Classification System [GMFCS-E&R], Wechsler Preschool and Primary Scale of Intelligence [WPPSI])
- Change from baseline in seizure frequency
- Change from baseline in neuroimaging
- Changes in growth parameters (body weight, body length, head circumference)
- Change from baseline in feeding patterns

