4.3. Safety

The safety of ORGN001 (formerly ALXN1101) will be assessed based on:

- Incidence and severity of adverse events (AEs) and serious adverse events (SAEs)
- Incidence of clinical laboratory abnormalities
- Change from baseline in clinical laboratory assessments
- Change from baseline in clinical findings from physical examination
- Change from baseline in vital sign measurements
- Change from baseline in electroencephalogram (EEG) results

In order to monitor subject safety, data will be reviewed daily by the PI or designee during the first 2 weeks following initiation of ORGN001. [REDACTED]

The SRC [REDACTED] will review all available clinical data [REDACTED] prior to each subject's scheduled dose escalations in conjunction with the data monitoring committee (DMC) [REDACTED] and at any other time during the study as requested by the PI or Sponsor.

Based on the review of the available data, [REDACTED] the SRC, in consultation with the DMC, may recommend stopping, increasing, decreasing, or maintaining (current dose) the dose of ORGN001.

In addition to the scheduled dose escalations, the PI may also convene the SRC for unscheduled dose adjustments based on drug-related AEs and changes in clinical parameters. The SRC chair will also convene the DMC if a dose escalation is being considered or will notify the DMC if the dose is decreased. Blood and urine samples will be collected for PD and PK assessments on the first day the adjusted dose is administered. PD and safety laboratory assessments will be repeated [REDACTED] at the [REDACTED] follow-up visit.

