6.2.2. Secondary Analyses**6.2.2.1. Neurologic Examination**

A summary of the frequency and percentage of subjects with neurologic examination findings [REDACTED] will be presented by visit.

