6.2.2.5. Feeding Patterns

The number and frequency of subjects able to feed orally will be summarized by visit. For subjects that are not feeding orally, the feeding method will be summarized by visit. Results will also be included in by-subject listings.

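### The EEG and feeding summaries, and in its visible text the neurologic one, give by-visit counts although the endpoints are changes from baseline, so within-patient change is left to listings

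*SAP*

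**What the plan says.** Three endpoints are defined as within-patient changes. SAP 4.3 lists "Change from baseline in electroencephalogram (EEG) results" under safety, as does protocol 2.2.1 ("Change from baseline in EEG results"). SAP 4.1 lists "Change from baseline in clinical findings from neurologic examination" and "Change from baseline in feeding patterns" under efficacy, in line with protocol 2.2.2.

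The SAP's planned summaries take a different form:

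- EEG (6.5.4.4): "The number and frequency of subjects with EEG findings will be summarized by visit".
- Feeding (6.2.2.5): "The number and frequency of subjects able to feed orally will be summarized by visit", with a further by-visit summary of feeding method for those not feeding orally.
- Neurologic examination (6.2.2.1): "A summary of the frequency and percentage of subjects with neurologic examination findings", by visit. A redaction falls in the middle of this sentence.

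Protocol 13.8.4 plans the same by-visit count for EEG. Protocol 13.7.2 names the feeding endpoint but gives no analysis for it. For the neurologic examination it is specific: "Shifts from baseline in clinical findings from neurologic examination and neuroimaging findings will be presented for the different time points". The synopsis makes the same commitment. The visible text of SAP 3.1 marks changes from the protocol's analyses as not applicable.

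By-subject listings are planned for all efficacy endpoints (SAP 6.2), for all safety data (6.5), and again specifically for feeding (6.2.2.5) and EEG (6.5.4.4).

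**The concern.** A count of children with a finding at each visit is a marginal summary. The endpoint is a paired quantity: how each child moved relative to his or her own baseline. The first does not determine the second, so for EEG and feeding the stated endpoint has no summary that expresses it. The same appears true of the neurologic examination.

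This bears on how the study will be read. Protocol 1.6 expects children to stay clinically stable after the switch from rcPMP and treats that as evidence of comparable efficacy. A percentage that is level from baseline to Month 6 will be read as stability, but it can also arise when some children improve and as many worsen. EEG change is in addition a listed safety endpoint, and safety is the primary objective.

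The SAP is also uneven on this point. It plans shifts from baseline for neuroimaging (6.2.2.4) and shift tables for laboratory tests (6.5.4.1).

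**Working it through.** The plan states no figure to reproduce: the study is descriptive, with no hypothesis test. The check has two parts.

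**1. Endpoint against planned summary**

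| Endpoint | Definition, both documents | Protocol analysis | SAP summary (visible text) | Listing |
|---|---|---|---|---|
| EEG | change from baseline | by-visit count (13.8.4) | by-visit count (6.5.4.4) | yes |
| Feeding | change from baseline | none specified (13.7.2) | by-visit count of oral feeding, plus method for the others (6.2.2.5) | yes |
| Neurologic examination | change from baseline | shifts from baseline (13.7.2, synopsis) | by-visit frequency and percentage (6.2.2.1, partly redacted) | yes |

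None of the three SAP summaries, as far as they can be read, pairs a visit with baseline. Only the neurologic row differs between protocol and SAP.

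**2. What the counts can and cannot show**

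Take n subjects assessed at both times. Let a have a finding at both, i lose a finding (improved) and w gain one (worsened). The by-visit table shows

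- baseline count = a + i
- visit count = a + w

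Subtracting gives w − i = visit count − baseline count. The net change is therefore known. The number of children who changed, w + i, is not.

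If both counts equal b, then w = i = k, where k can be any whole number from 0 to min(b, n − b). The number who changed is 2k, and min(b, n − b) + 1 different shift tables fit the same counts.

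The planned minimum is n = 4 (protocol 13.2). The values of b are assumptions, so the whole range is shown:

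| b of 4 at both times | Largest k | Shift tables that fit | Children changed |
|---|---|---|---|
| 0 or 4 | 0 | 1 | 0 |
| 1 or 3 | 1 | 2 | 0 or 2 |
| 2 | 2 | 3 | 0, 2 or 4 |

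At 2 of 4, the table reads 50% and 50% whether no child changed, one improved and one worsened, or two improved and two worsened. With an assumed n = 8 and 4 of 8 at both times, min(4, 4) + 1 = 5 tables fit, and up to 8 children may have changed.

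The masking therefore occurs when the count lies strictly between 0 and n. At 4 of 4 on both occasions no child can have crossed the line between normal and abnormal. What stays hidden there is change in degree among children who remain abnormal, and a plain normal/abnormal shift table would hide that too.

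EEG has a further difficulty. In the Extension Period EEGs are done only when there is a clinical reason (protocol Table 6 footnote 9). Later counts then come from a selected subset and are not comparable with the baseline count even as marginals.

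**The case against.** The strongest reply is that nothing is lost. By-subject listings cover all three endpoints, and with about 4 children a reader can set each child's baseline beside each later visit. That stands, and it limits the point to the summary tables. A reader might infer that offsetting changes cannot be seen at all, and the listings rule that out. But a listing leaves the reader to judge who improved or worsened after the data are known, whereas a prespecified shift table fixes the categories in advance.

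Other stronger readings also fail:

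- **That the SAP departs from the protocol throughout.** For EEG it follows protocol 13.8.4. For feeding the protocol specifies no analysis. Only the neurologic examination carries a protocol promise of shifts.
- **That the neurologic shifts have certainly been dropped.** The key SAP sentence is partly redacted, and much appendix material is blacked out. One can say only that the visible text lacks them.
- **That the tables report nothing beyond the presence of a finding.** Feeding method is also tabulated.
- **That by-visit counts stay flat whatever happens.** Any net movement across the line shifts them. If most children are abnormal at baseline, there is also less room for offsetting changes: at most one pair at 3 of 4, and none at 4 of 4.

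The safety consequence is limited as well. Worsening of a pre-existing condition is to be recorded as an adverse event (protocol 12.5.1), and seizures recorded that way are summarized as such (SAP 6.2.2.3).

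**Conclusion.** The point holds as a gap between endpoint and summary table. For EEG and feeding this is plain from unredacted text. For the neurologic examination it holds for the visible text, and there the protocol's shift analysis is neither shown nor declared as changed in SAP 3.1. For EEG the gap is in both documents, so it is not a SAP departure.

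The size is modest. At n = 4 the worst case is 2 of 4 at both times, which is compatible with 0, 2 or 4 children changed. The 2 of 4 is an assumption, because the documents give no baseline distribution. Individual changes remain readable in the listings. The change is still worth making, since the present summaries cannot express the stated endpoints and the protocol's efficacy argument rests on individual stability.

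**What to change.** In SAP 6.2.2.1, 6.2.2.5 and 6.5.4.4, add baseline-by-visit shift tables to the by-visit counts:

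- feeding: oral / nasogastric / gastrostomy;
- EEG: normal / abnormal;
- each neurologic domain: normal / abnormal.

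Restrict each table to subjects with both a baseline and a visit assessment, and show that number. This matters most for Extension Period EEGs. Use the baseline already defined in SAP 8.3, the last assessment before ORGN001.

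Beside each table, give counts improved / unchanged / worsened, so that change among children who remain abnormal is also captured. State beforehand how that classification is made from the recorded findings, including how moves between the two tube-feeding categories are counted.

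If the neurologic shift analysis was dropped on purpose, declare it in SAP 3.1. If it sits in redacted text, confirming that settles the neurologic part.

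The cost is SAP wording, the classification rule and three sets of shift tables from data already planned for collection.

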8. APPENDICES

8.3. Technical Specifications for Derived Variables

The following derived data will be calculated prior to analysis.

Age

Age will be presented as the number of days or months between date of birth and the reference date and will be calculated as follows:

Age in days: (Visit date – date of birth) + 1 day

Age in months: ((Visit date – date of birth) + 1 day)/30.4375

The following ages in [Table 3](#) may be computed, with reference dates indicated.

Table 3: Age and Reference Date

AGE	REFERENCE DATE
Age at study enrollment (months)	• Date of signing ICF
Age at first symptom (days)	• Date of first symptoms
Age at first ORGN001 infusion (days)	• Date of first infusion
Age at each developmental assessment (months)	• Date of developmental assessment

If the reference date is not complete, then age at reference date will be determined by the month and/or year of date of birth and reference date.

Weight and Height

Weight in pounds will be multiplied by 0.4536 to be converted to kilograms; and height in inches will be multiplied by 2.54 to be converted to centimeters.

The BMI will be calculated by dividing the subject's weight in kilograms by the subject's height in meters squared. The units are kg/m².

BQL and LLOQ Values for Clinical Laboratory Parameters

For all clinical laboratory parameters, values that are reported as below quantification level (BQL) or lower limit of quantification (LLOQ) will have numeric values set equal to the BQL or LLOQ lower limit (e.g., if BQL <2, then value will be set equal to 2). However, the original value will be displayed in by-subject data listings.

Date of Infusion

Date of first ORGN001 infusion, as well as date of last ORGN001 infusion will be derived.

Time from First Infusion to Applicable Assessments (Days)

For all applicable assessments, time on treatment from first infusion will be calculated as follows:

- If visit date is on or after first infusion = (Visit date – Day 1 Infusion date) + 1 day
- If visit date is prior to first infusion = (Visit date – Day 1 Infusion date)

Time from First Infusion to Applicable Assessment (Months)

For all applicable assessments, time on treatment from first infusion will be calculated as follows:

- If visit date is on or after Day 1 infusion = ((Visit date – Day 1 Infusion date) + 1 day)/30.4, rounded to 1 decimal place
- If visit date is prior to Day 1 infusion = (Visit date – Day 1 infusion date)/30.4, rounded to 1 decimal place

Time on Study (Days)

For each subject, time on study from informed consent to last visit, study completion, termination or withdrawal (days) will be calculated as follows:

- For subjects who completed Month ■ = (date of Month ■ visit date – date of informed consent) + 1 day
- For subjects who withdrew prior to Month ■ = (date of study exit – date of informed consent) + 1 day

Additionally, for each subject, time on study from informed consent to last infusion will be similarly calculated.

Time on Study (months)

For each subject, time on study from informed consent to last visit, study completion, termination or withdrawal (months) will be calculated as follows:

- For subject who completed Month ■ = ((date of Month ■ visit date – date of informed consent) + 1 day)/30.4375, rounded to 1 decimal place
- For subjects who withdrew prior to Month ■ = ((date of study exit – date of informed consent) + 1 day)/30.4375, rounded to 1 decimal place

Additionally, for each subject, time on study from informed consent to last infusion will be similarly calculated.

Definition of Baseline Values

Baseline is defined as the last available assessment prior to treatment with ORGN001, except for growth parameters and blood and urine ■ where baseline is defined as the average of all available assessments on or prior to the date of first infusion with ORGN001.

Change from Baseline

Change from baseline will be calculated as follows:

Change of Baseline = Assessment Value – Baseline Assessment Value

Percent Change in Assessments from Baseline

Percent change in values from Baseline will be calculated as follows:

$$\% \text{ Change in Value} = \frac{(\text{Change in Value})}{\text{Baseline value}} \times 100$$

where Change in Value = (Assessment value – Baseline Assessment value), given that the baseline value is non-missing and non-zero and the subsequent value is non-missing.

Adverse Events

The analysis of AEs is described in detail in [Section 6.5.3](#). Subject percentages are based on the total number of treated subjects in the Safety Set.

Related AEs are defined as possible, probable, definitely related or unknown/missing. Unrelated AEs are defined as unlikely or not related.

A pre-treatment AE refers to an AE that occurred prior to first ORGN001 infusion. Treatment-emergent AEs are events with start dates and start times on or after the date and time of the first ORGN001 infusion. If the start date of an AE is partially or completely missing and the end (stop) date and time of the AE does not indicate that it occurred prior to first infusion, then the determination of treatment-emergent status will be based on the following:

- If the start year is after the year of the first study drug infusion, then the AE is treatment-emergent; else,
- If the start year is the same as the year of the first study drug infusion and
 - the start month is missing, then the AE is treatment emergent; else if
 - the start month is present and is the same or after the month of the first study drug infusion, then the AE is treatment-emergent; else.
- If the start date is completely missing, then the AE is treatment-emergent.

All other AEs are considered PTAEs.

Child-Pugh Score

Child-Pugh score will be calculated as follows:

The total of the clinical or biochemical measurement scores (1, 2 or 3) according to [Table 4](#) determines the Child-Pugh score as Grade A (5-6), Grade B (7-9), or Grade C (10-15).

Table 4: Criteria for Child-Pugh Classification

Clinical or Biochemical Measurements	Points Scored for Increasing Abnormality		
	1	2	3
Hepatic encephalopathy (grade)	Absent	1 and 2	3 and 4
Ascites	Absent	Mild	Moderate
Total bilirubin (mg/dl)	<2.0	2.0-3.0	>3.0
Serum albumin (g/dl)	>3.5	2.8-3.5	<2.8
Prothrombin time INR	<1.7	1.7-2.3	>2.3

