## 10 PHARMACODYNAMIC ASSESSMENTS

Pharmacodynamic biomarker assessments will be performed [REDACTED]. An alternative blood sampling schedule for infants weighing less than 10 kg, for whom less blood volume should be collected, must be used [REDACTED].

Urine samples will be collected [REDACTED]. An additional optional urine sample may be collected [REDACTED] for PD assessment at the visit on Day 1. [REDACTED]

Venous blood samples will be collected [REDACTED]. In addition, a PD blood sample will be collected prior to the ORGN001 infusion at one time between Month 7 and the last month of the Extension Period. [REDACTED]

Samples will be evaluated for biomarkers of the MoCD pathway, which may include, but are not limited to, SSC, [REDACTED] levels. [REDACTED]

During the Screening Period (Day -21 to Day -1), both urine and blood samples must be collected [REDACTED], in order to calculate baseline levels. On Day 1, a urine sample and a blood sample are to be collected prior to the first infusion. [REDACTED]

Following recommendation by the SRC for an unscheduled dose adjustment during the 6-Month Initial Treatment Period, or after dose escalation is complete and the patient is returned to a prior dose, additional blood and urine samples will be collected to evaluate the changes in SSC, [REDACTED], uric acid, urinary creatinine, [REDACTED]:

- On the first Day the adjusted dose is administered, as well as [REDACTED] at the [REDACTED] Follow-up Visit, the patient will be administered study drug in-clinic, and a blood sample will be collected at 3 to 4 hours after the EOI. A urine sample will be collected at any time during the study visit.
- If either visit coincides with a previously scheduled PD sample collection, only 1 PD blood sample [REDACTED] and 1 PD urine sample [REDACTED] should be collected at that visit.

Under no circumstance will the total blood volume obtained exceed the amount considered acceptable for the patient's clinical condition and the institution's guidelines [REDACTED]. If an Investigator decides to deviate from these limits, the deviation must be fully documented, and the Investigator should provide justification for the deviation. [REDACTED]

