3.1. Changes from Analyses Specified in the Protocol

Not applicable.

[REDACTED]

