6.2.2.6. Growth Parameters

Body weight, length, head circumference, and body mass index (BMI) will be analyzed by converting each parameter to age-adjusted z-scores and age percentiles and descriptive statistics will be presented for each parameter, as well as, for the change from baseline. The 5th, 25th, 50th, 75th, 90th, and 95th percentiles will be calculated.

Weight, length, head circumference, and BMI data including age-adjusted z-scores and percentile for each growth parameter-for-age will be presented in a by-subject data listing.

In addition, the following individual subject's growth charts will be produced with a flag for start of ORGN001 infusion and will include a symbol representing dose changed, if applicable: weight-for-age percentiles, length-for-age percentiles, head circumference-for-age percentiles, and BMI-for-age percentiles.

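### SAP 8.3 departs from the protocol's baseline definition for growth and biomarkers without a visible declaration, leaving the growth averaging scale unstated and the Day 1 cut-off loose

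*SAP*

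**What the plan says.** **Protocol 13.7.2.** The general rule is the last value: "Baseline is defined as the last available assessment prior to treatment with ORGN001 except for blood and urine biomarkers". For those biomarkers, "baseline is defined as the average of all available assessments prior to treatment with ORGN001". Growth is not in the exception, so it takes the last value before ORGN001.

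**SAP 8.3, Definition of Baseline Values.** The general rule is again the last value, but the exception is wider: "except for growth parameters and blood and urine". The next word is blacked out; I read it as biomarkers, by comparison with the protocol. For this whole group the SAP continues: "where baseline is defined as the average of all available assessments on or prior to the date of first infusion with ORGN001".

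**SAP 3.1.** Under changes from the protocol's analyses, the visible text is "Not applicable".

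**Where these baselines are used.** SAP 6.2.2.6 analyses growth by "converting each parameter to age-adjusted z-scores and age percentiles", with descriptive statistics for each parameter and for its change from baseline. SAP 6.2.2.7 summarises the value, change and percentage change of urine and blood biomarkers by visit.

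**Day 1 biomarker samples.** Protocol 10 and Table 3, footnote 27, place the required Day 1 samples before the first infusion. Protocol 10 also says "An additional optional urine sample may be collected" at the Day 1 visit, with its timing blacked out. Table 3, footnote 35, describes an optional blood and urine sample 24 hours after the end of infusion.

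**The concern.** Two documents that should give one baseline give two, and the later one does not say that it changed anything. In a growing child, the mean of several earlier weights or lengths lies below the most recent one, so a raw change measured from the mean is larger. For biomarkers, a calendar date cannot separate a sample taken before the first infusion from one taken after it on the same day.

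The study is open-label and noncomparative (Protocol 1.6), enrols at least 4 patients (Protocol 13.2), tests no hypothesis (Protocol 13.1) and plans no sensitivity analysis (SAP 6.2.1.5). Descriptive change from baseline therefore carries much of the evidence on growth and SSC. No control arm would cancel a baseline artefact, and no planned analysis would expose it.

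**Working it through.** The documents give no figure to reproduce. The check is a comparison of the two texts, followed by sensitivity arithmetic under stated assumptions.

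**1. The two definitions side by side**

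| Item | Protocol 13.7.2 | SAP 8.3 |
|---|---|---|
| Growth baseline | Last value | Average |
| Biomarker baseline | Average | Average |
| Cut-off for averaged values | Before treatment | Up to and including the calendar date of first infusion |

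Rows 1 and 3 differ.

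**2. Raw growth values averaged**

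Inputs: screening runs from Day -21 to Day -1 with at least two visits (Protocol Table 3, footnote 3); first dose is on Day 1; the period ends on Day 180. There is no Day 0, so with Day 1 set to elapsed day 0, Day 180 is elapsed day 179. Assumptions: linear growth, and the visit patterns below, because the growth schedule is blacked out.

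Lag = last pre-dose day minus mean pre-dose day. Excess = lag / (179 - last pre-dose day). The growth rate cancels.

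| Pre-dose measurements (elapsed days) | Lag (days) | Excess in 6-month raw change |
|---|---|---|
| -2, -1 | 0.5 | 0.5/180 = 0.3% |
| -7, 0 | 3.5 | 3.5/179 = 2.0% |
| -21, -1, 0 | 7.33 | 7.33/179 = 4.1% |
| -21, -1 | 10 | 10/180 = 5.6% |
| -21, 0 | 10.5 | 10.5/179 = 5.9% |
| -21, -20, 0 | 13.67 | 13.67/179 = 7.6% |
| One measurement only | 0 | 0% |

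**3. Z-scores averaged, each at its own visit age**

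Assume z drifts linearly by *d* over the 179 days and the last pre-dose measurement is on Day 1. The shift in reported change is *d* × lag / 179.

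- *d* = 0: shift 0.
- *d* = +0.5: 0.5 × 7.33/179 = +0.02 (pattern -21, -1, 0) and 0.5 × 10.5/179 = +0.03 (pattern -21, 0).
- *d* = -0.5: -0.02 and -0.03.

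The shift follows the drift. A child falling behind is shown as falling slightly further.

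**4. Raw values averaged, then converted to z**

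The result depends on the age paired with the averaged value, which the SAP does not state. With age at first infusion, baseline z in a growing child is too low by (days by which the mean precedes first infusion) × (growth per day) / (reference SD), and change in z is too high by that amount. The documents give neither growth rate nor reference SD, so I put no number on it.

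**5. One same-day post-infusion biomarker sample in the baseline**

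Assume *m* pre-dose samples at level 1, one post-dose sample at 1 + *s*, and later visits also at 1 + *s*. Baseline = (*m* + 1 + *s*)/(*m* + 1). Reported change = (1 + *s*)/baseline - 1.

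| True change *s* | *m* = 3 | *m* = 2 |
|---|---|---|
| -20% | 0.80/0.950 - 1 = -15.8% | 0.80/0.9333 - 1 = -14.3% |
| -50% | 0.50/0.875 - 1 = -42.9% | 0.50/0.8333 - 1 = -40.0% |
| +20% | 1.20/1.050 - 1 = +14.3% | 1.20/1.0667 - 1 = +12.5% |
| 0% | 0% | 0% |

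Any change, up or down, shrinks toward zero. The values of *s* are assumptions.

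**The case against.** The strongest reply is that the planned growth scale is the z-score, in both documents, and no passage explicitly plans a change in kilograms or centimetres. On own-age z-scores the averaging does almost nothing. This largely stands. A reader might infer that growth change is overstated, or that the error always favours the drug. The documents do not support either: the shift can be zero, or go against the drug when z falls. What survives is that the SAP never says whether z-scores or raw values are averaged, or which age goes with an averaged raw value.

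A reader might also infer that, since every available assessment counts, old clinic measurements could enter the average. The support is weak. Screening is limited to Days -21 to -1, study procedures may not precede consent, and the visible text accepts earlier results only for MRI, EEG, genotype, and vision and hearing records. The pre-dose growth schedule is blacked out, so it is not even shown that growth is measured more than once before dosing.

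On biomarkers, a reader might infer that post-dose Day 1 samples do enter baseline. That is not shown. The required Day 1 samples are pre-infusion, and a sample 24 hours after the end of infusion normally falls on the next date, which the SAP rule excludes. The date wording has a sensible purpose, to capture Day 1 pre-infusion samples. Patients also switch from rcPMP at the same dose, so a post-dose shift may be small. Still, the wording permits what the protocol's wording excludes, and the timing of the optional Day 1 urine sample cannot be read.

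Finally, individual values are listed and biomarker and growth courses plotted, so no reader depends on the averaged baseline alone. That limits the harm but leaves two conflicting definitions in place.

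**Conclusion.** The point holds as an undeclared inconsistency with small or conditional numerical effects. SAP 8.3 averages growth where the protocol does not, and it includes the whole calendar day of first infusion where the protocol stops at treatment. Nothing visible in SAP 3.1 declares either change.

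Under linear growth and the assumed visit patterns, the effect on raw 6-month growth change is roughly 0.3% to 7.6%, and nil with one pre-dose measurement. For own-age z-scores it is zero if z is stable, and about ±0.02 to 0.03 for a drift of ±0.5. Which case applies cannot be settled from the SAP, so two programmers could produce different baselines from the same data.

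The biomarker effect is attenuation toward zero, conditional on a same-day post-infusion sample that the wording allows but the documents do not show to exist. The point merits correction because the baseline feeds every change reported for growth and SSC and the remedy is short.

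**What to change.** In SAP 8.3:

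1. Remove growth parameters from the averaging exception, so that the last pre-infusion measurement is used as in Protocol 13.7.2. If averaging is intended, average z-scores computed at each visit's own age, say so, and list the change in SAP 3.1.
2. Replace the calendar-date cut-off with *before the start of the first infusion*. Apply it by collection time or, where no time was recorded, by the scheduled pre-infusion label of the Day 1 sample. The fallback is needed because the visible text asks for recorded times for dosing and PK samples, but not for urine biomarker samples or growth measurements.

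SAP 8.3 already classifies treatment-emergent adverse events by the date and time of the first infusion, so a time-based cut-off is not new to the plan. The cost is a minor SAP edit and a check of Day 1 sample timing; no new data are needed.
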